## Unanticipated Adverse Events

An unanticipated problem is any event or information that was unforeseen and indicates that the research procedures caused harm (including physical, psychological, economic, or social harm) to participants or others or indicates that participants or others are at increased risk of harm than was previously known or recognized. An "unexpected" adverse reaction is one in which the nature or severity of which is not consistent with information in the relevant source document(s). Until source documents are amended, expedited reporting is required for additional occurrences of the reaction. Relationship to Study Drug

The relationship or association of the AE/SAE to study drug will be characterized as "related" or "not related." An AE/SAE will be considered to be not related to the use of the study drug if any of the following criteria are met:

• An unreasonable temporal relationship between administration of the product and the onset on the AE (e.g., the event occurred either before, or too long after administration of the product for it to be considered product-related);

- A causal relationship between the product and the AE is biologically implausible (e.g., death as a passenger in an automobile accident);
- A clearly more likely alternative explanation for the AE is present (e.g., typical adverse reaction to a concomitant drug).

Adverse events will be considered "related" to the use of the study drug if none of the "not related" criteria are met. The Investigator will use clinical judgment to determine the relationship of the AE/SAE to study drug. An AE/SAE may be related to the study drug, other concomitant medications, intercurrent illness, a procedure performed in the course of the study, or another reason. Among the potential etiologies, the Investigator will make a determination based on the most likely causal relationship. Alternative causes, such as the natural history of any underlying diseases, concomitant therapy, other risk factors, and the temporal relationship of the event to the study drug will be considered. The Investigator will also take into account the Investigator's Brochure in the causality assessment. There may be situations when an SAE has occurred and the Investigator will make an assessment of causality prior to transmission of the SAE report to the Sponsor, as the causality assessment is one of the criteria used when determining regulatory reporting requirements. The Investigator may change the causality assessment in light of follow-up information by amending the SAE report accordingly.

SAEs that are considered related (i.e., determined to be possibly, probably, or definitely related) to the investigational product by the Sponsor-Investigator will be followed until the event resolves or stabilizes. Any SAE that occurs after treatment completion, and is considered by the Sponsor-Investigator to be related to the investigational product, will be documented and reported as appropriate.

Reporting Serious Adverse Events to Regulatory Agencies

Events meeting the following criteria will be submitted to the Food and Drug Administration (FDA) as expedited IND Safety Reports according to the following guidance and timelines: 7 Calendar Day Telephone or Fax Report

The Sponsor-Investigator will notify the appropriate review division at the FDA of any fatal or lifethreatening adverse event that is unexpected and assessed by the Sponsor-Investigator to be possibly related to the use of the investigational product. An unexpected adverse event is one that is not already described in the investigational product's Investigator Brochure. Such reports are to be telephoned or faxed to the appropriate review division at FDA and to the manufacturer of the investigational product within seven calendar days of first learning of the event.

15 Calendar Day Written Report

The Sponsor-Investigator will notify the appropriate review division at the FDA, in a written IND Safety Report, of any serious, unexpected AE that is considered reasonably or possibly related to the use of the investigational product.

Written IND Safety reports will include an Analysis of Similar Events in accordance with regulation 21 CFR § 312.32. All safety reports previously filed by the Sponsor-Investigator with the IND concerning similar events will be analyzed and the significance of the new report in light of the previous, similar reports commented on.

Written IND safety reports with Analysis of Similar Events will be submitted to the appropriate review division at the FDA, and the manufacturer of the investigational product within 15 calendar days of first learning of the event, using FDA Form 3500A.

Written IND Safety Reports will be submitted to the IRB(s) of record per IRB Guidelines. IND Annual Reports

The Sponsor-Investigator will provide annual reports to the appropriate review division at the FDA within 60 days of the IND's anniversary date, until the IND is withdrawn or terminated.

### C.7 Risks of Study Drug:

A review of 25 studies on the safety and efficacy of CBD did not identify significant side effects across a wide range of dosages, including acute and chronic dose regimens, using various modes of administration [Bergamaschi M.M., et al. 2011]. There are no rare but serious side effects reported. The most frequently occurring side effect was somnolence (i.e.drowsiness) (25%). Other side effects, in order of prevalence, include: diarrhea (19%), decreased appetite (19%), fatigue (13%), convulsion (11%), increased appetite (9%), status epilepticus (8%), lethargy (7%), weight increased (7%), and weight loss (6%) [Devinsky O, et al. 2016]. Other side effects include extrapyramidal symptoms, increased prolactin levels, weight gain, increased serum concentrations of antiepileptic drugs, and elevated liver function tests.

Table 6 and 7 show the adverse reactions of pure CBD, i.e., Epidiolex®.

**Table 6.** Adverse events and treatment-emergent serious adverse events of purified CBD reported in pediatric treatment-resistant epilepsy (an open-label interventional trial, maximum dose 25-50 mg/kg/day of CBD) [Devinsky O, et al. 2016]

ing/kg/day of CDD) [Devinsky 0, et al. 2010]	
Adverse events (reported >5% of patients)	N =162
Somnolence	41 (25%)
Decreased appetite	31 (19%)
Diarrhoea	31 (19%)
Fatigue	21 (13%)
Convulsion	18 (11%)
Increased appetite	14 (9%)
Status epilepticus	13 (8%)
Lethargy	12 (7%)
Weight increased	12 (7%)
Weight decreased	10 (6%)
Drug concentration increased	9 (6%)
Treatment-emergent serious adverse events	
Status epilepticus	9 (6%)
Diarrhoea	3 (2%)
Weight decreased	2 (%)
Convulsion	1 (<1%)
Decreased appetite	1 (<1%)
Drug concentration increased	1 (<1%)
Hepatotoxicity	1 (<1%)
Hyperammonaemia	1 (<1%)
Lethargy	1 (<1%)
Unspecified pneumonia	1 (<1%)
Aspiration pneumonia	1 (<1%)
Bacterial pneumonia	1 (<1%)
Thrombocytopenia	1 (<1%)

**Table 7.** Adverse events occurring with a frequency of greater than 10% in either trial group (RCT in 120 children and young adults with the Dravet syndrome and drug-resistant seizures, 20 mg/kg/day of CBD) [Devinsky O, et al. 2017]

System Organ Class and Preferred Term	Cannabidiol (n=61)	Placebo (n=59)
Gastrointestinal		
Diarrhea	19 (31%)	6 (10%)
Vomiting	9 (15%)	3 (5%)
General		
Fatigue	12 (20%)	2 (3%)
Pyrexia	9 (15%)	5 (8%)
Infections: upper respiratory tract infection	7 (11%)	5 (8%)
Metabolism: decreased appetite	17 (28%)	3 (5%)
Nervous system		
Convulsion	7 (11%)	3 (5%)
Lethargy	8 (13%)	3 (5%)
Somnolence	22 (36%)	6 (10%)

#### **D.** Description, Risks and Justification of Procedures and Data Collection Tools:

Patients could be uncomfortable about their survey of cannabis, drug, alcohol, and tobacco use that is administered during screening in both Stages. However, this information is essential for their safety, to check for history of addiction, and if this is found then the participant could be harmed by participating and thus would be excluded. In addition, this information is needed for scientific rigor. Federal funding sources are likely to want this information to understand the relevance and importance of future cannabis studies. The importance of having the information will be explained and the participant will be reminded that participation is voluntary.

CBD's effect on many aspects of PD are being studied, besides the primary and major secondary outcome measures. This makes the visits longer and may be tiring for some participants. To minimize discomfort participants will be offered sufficient breaks and maximal efforts for efficiency will be made to minimize visit time. The reason for the many assessments is twofold. First, PD is a complex disorder with many different disabling symptoms, and secondly, it is prudent to maximize the information from this study. Studies on cannabis are sorely needed, since many PD patients are taking this potentially dangerous drug as it becomes more available. Access is becoming more available throughout the US as more states are considering legalizing use of medical and recreational marijuana. Besides this lack of vital information, obtaining funding and getting through all the regulatory steps required for study of cannabis is very hard, thus we want to obtain maximal information when such a study (as this one) can be done. This information is vital to guide future studies.

To minimize the risk in the study, the following procedures will be complied with:

- 1. The study will be conducted in compliance with the COMIRB approved protocol, GCP, and the applicable regulatory requirements.
- 2. The study will be overseen by COMIRB and a Data Safety Monitoring Board (DSMB) at University of Colorado.
- 3. Each patient will be closely monitored by frequent clinic visits during study drug treatment phases and the 7th day following discontinuation of study drug as described in Section C to

monitor for adverse effects or withdrawal, as well as changes of medical history and concomitant medications.

- 4. Adverse events and serious adverse events will be reported from the time of study drug administration until the last study visit or death, whichever occurs first, according to mandated guidelines.
- 5. All adverse events and serious adverse events will be followed until resolution (or return to baseline status), or until the condition stabilizes or is otherwise explained, or until participant dies or is lost to follow-up.
- 6. Safety assessments are comprehensive and include vital signs, history and physical examination, concomitant medications collection, EKGs, safety labs (Hematology, Hemoglobin A1C, Complete Metabolic Profile and Liver Function Tests), blood and urinary cannabis and metabolites analysis, MoCA, QUIP-RS, C-SSRS, NPI, SCOPA-sleep, Anxiety short form, Depression short form, Emotional and behavioral dyscontrol short form, Fatigue Severity Scale, Pain Intensity and Interference short form, study drug compliance check, adverse event check, and urine and blood pregnancy testing.

We will follow the FDA's Guidance for evaluating and monitoring potential drug-induced hepatotoxicity. Participants with stable liver disease can be included if they have a normal total bilirubin and prothrombin time/INR at baseline. Liver function tests (ALT, AST, ALP and bilirubin) will be drawn at baseline and at each visit while participants are on the study drug. In addition, if these labs are abnormal at the end of the study visit they will be repeated at the safety follow up visit two weeks later and repeated until back to baseline values. During each visit that assesses the effects of the study drug, nonspecific symptoms of Drug Induced Liver Injury (DILI) will be checked, e.g., anorexia, nausea, fatigue, right upper abdominal discomfort, and vomiting. If symptoms indicative of DILI occur, the participant will return to clinic immediately for measurement of laboratory signs of hepatic injury, regardless of when the next visit or monitoring interval is scheduled. At any time if aminotransferase enzymes are greater than three times the upper limit of normal (ULN), we will repeat ALT, AST, ALP, and bilirubin within 48-72 hours. If symptoms persist or repeat testing shows aminotransferase >3xULN for participants with normal baseline measures or twofold increases above baseline values for participants with elevated values before drug exposure, we will initiate close observation to determine whether the abnormalities are improving or worsening. Per the FDA, close observation includes:

- Repeating liver enzyme and serum bilirubin tests two or three times weekly. Frequency of retesting can decrease to once a week or less if abnormalities stabilize or the trial drug has been discontinued and the participant is asymptomatic.
- Obtaining a more detailed history of symptoms and prior or concurrent diseases.
- Obtaining a history of concomitant drug use (including nonprescription medications and herbal and dietary supplement preparations), alcohol use, recreational drug use, and special diets.
- Ruling out acute viral hepatitis types A, B, C, D, and E; autoimmune or alcoholic hepatitis; NASH; hypoxic/ischemic hepatopathy; and biliary tract disease.
- Obtaining a history of exposure to environmental chemical agents.
- Obtaining additional tests to evaluate liver function, as appropriate (e.g., INR, direct bilirubin).
- Considering gastroenterology or hepatology consultations.

We will gather further history as recommended. Unless we find that the repeat testing shows the aminotransferase levels decline to baseline, we will consult the UCH Hepatology team to determine further management.

The FDA advises that since transient fluctuations of ALT or AST are common and progression to severe liver injury or failure is uncommon, automatic discontinuation of trial drug upon finding a greater than 3xULN elevation of ALT or AST may be unnecessary. The decision of whether to stop the study drug will be affected by information on related drugs, the accumulating clinical experience, the clinical status of the patient, and many other factors. We will consult the UCH hepatology service and keep the following FDA guidance in mind. The FDA states that discontinuation of treatment should be considered if:

ALT or AST >8xULN

ALT or AST >5xULN for more than two weeks

ALT or AST >3xULN and (TBL >2xULN or INR >1.5)

ALT or AST >3xULN with the appearance of fatigue, nausea, vomiting, right upper quadrant pain or tenderness, fever, rash, and/or eosinophilia (>5%)

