#### Discussion

The primary outcome was safety and tolerability. Generally, the study drug, Epidiolex®, was well tolerated. While adverse effects, mainly somnolence, fatigue, and diarrhea, were frequent, they were generally mild, and there was a relatively low percent of participants, i.e., 23%, that stopped study drug due to intolerability, and no clinically significant abnormalities in testing except for elevated liver enzymes.

Regarding the elevated liver enzymes, GW had seen elevations in their pediatric group, but the pattern was hepatocellular, not cholestatic as in our population. Perhaps age contributed to the difference, since GW had not used Epidiolex® in persons over age 50. In our study liver enzymes were only checked on the highest dose and most of the affected participants were asymptomatic, so it is not clear at what dose the liver enzymes became elevated. [name], Hepatologist, reviewed detailed information on these participants and of all the liver function results in all participants, commented that the changes may represent early liver injury and felt that with close monitoring it was reasonable to move on with the next study. She will be a consultant on the randomized controlled parallel study. The DSMB also reviewed all the data and noted that all changes resolved with cessation of treatment and discussed the possibility the elevations may be related to medication vehicle, i.e., sesame oil. Most participants were talking 10-20 ml per day on the final maximal dose when the testing occurred. The DSMB agreed with continuation of the study with the monitoring plan in this protocol.

Solid conclusions regarding efficacy are not possible from an open label trial, but this study suggested benefit in motor symptoms, night-time sleep, and emotional dyscontrol.

In summary, findings from the open label study suggest that CBD may be efficacious in PD, and that a lower dose may offer the best benefit to risk ratio, compared to the higher dose that GW reports is useful in pediatric epilepsy. Therefore, a lower dose will be used in the randomized controlled parallel study.

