We considered other factors while choosing a study drug to use in the randomized controlled parallel study. While Epidiolex® was the best option for our open label dose-escalation study, we recognized that a disadvantage of using a pure CBD preparation and such a high dose is that it is different from what persons with PD obtain from local dispensaries. While local dispensaries sell cannabis that is

high in CBD, their products are not pure CBD and markedly lower doses are used, so our findings would not be very applicable to the products our PD patients are taking. The study drug and dosage to be used in the randomized controlled parallel study will be more similar to what persons with PD are obtaining from local dispensaries. Another consideration is that THC, CBD, and the other components of the cannabis plant interact, e.g., the "entourage" effect, and this interaction may have a meaningful effect, which would not be occurring in Epidiolex® since it is such a pure CBD product.

Therefore, we will use a cannabis extract with 59.3% CBD and 1.96% THC (30:1 CBD:THC) from NIDA. We will give 1.25 mg/kg twice daily of CBD and 0.041 mg/kg twice daily of THC. This equals 2.11 mg/kg twice daily (4.22 mg/kg/day) of the NIDA extract. For our average sized PD participant (84 kg) in our prior trial this will be approximately 100 mg CBD and 3.3 mg THC twice daily (morning and evening - > 6 hours apart). Therefore, the THC dose is below the threshold, ~5mg, that is expected to cause a person to feel "high." The interval of >6 hours is to minimize the possibility of the THC effect to overlap/build up. The extract solution will be in a sesame oil formulation, 100 mg/ml of CBD, so the participant would ingest 1 ml (100 mg CBD) twice daily. This much smaller amount of CBD and of oil is expected to be better tolerated, including less likely to cause liver enzyme elevations, than the study drug in the open label study.

In comparison to the open label study, the amount of CBD in this study is less than 15% (19.23/2.5). This dose and the fact that there is a small amount of THC is in the product makes this study drug more similar to what persons are receiving from local dispensaries, although it may generally have a higher in CBD content. Therefore, the results of the study using this product will be more generalizable to the Colorado PD population.

Whether participants should be allowed to drive has been carefully considered:

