#### **Secondary Outcome Measures:**

**1**. To evaluate the safety and tolerability of CBD in PD:

1.1 By examining the frequency of study-related adverse events at each dose level between the two groups (treatment vs. placebo). Adverse events are measured at study visits, starting with an open ended question (Do you notice any effects, good or bad, of the study drug?) and followed by a series of yes/no questions regarding adverse effects (including previously reported adverse effects of CBD and general common adverse effects of medications and the hepatotoxicity), and all the effects we hypothesize in the study. For each adverse and beneficial reported effect, further questions will be asked, such as when did the effect start and how is it progressing, etc. In addition, since a major dose limiting effect is somnolence, the daytime sleepiness part of the SCOPA-sleep is included.

Tolerability is judged and supervised by PI and sub-I (who are MDs), based on their clinical expertise.

Abuse-related AEs will also be collected at screening, each dose assessment visit, liver function monitoring visit, and safety follow up visit. The abuse-related AEs is provided by MedDRA Preferred Terms (PTs), including:

Euphoria-related terms: Euphoric mood, elevated mood, feeling abnormal, feeling drunk, feeling of relaxation, dizziness, thinking abnormal, hallucination, inappropriate affect. Terms indicative of impaired attention, cognition, and mood: Somnolence, mood disorders, and disturbances.

Dissociative/psychotic terms: Psychosis, aggression, confusion, and disorientation. Related terms not captured elsewhere: Drug tolerance, habituation, drug withdrawal syndrome, substance-related disorders.

The Abuse-related AEs will be collected and recorded on a CRF that includes timing of the event, duration, severity, indication if more than one event was observed simultaneously, if other drugs were taken by subjects at the time of the event, correlation between the onset of the event, and the use of study drug.

Well trained investigators will capture and report cases of abuse, misuse, or addiction and monitor for drug accountability discrepancies before starting trials.

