- 1.2 Liver monitoring plan: Liver function tests (including Alk Phos, ALT, AST, GGT, Total Bili) will be tested at each dose during treatment phase. Study participants will be asked to check for symptoms of hepatotoxicity when on study drug. A Hepatology consultant, [name]., has agreed advise on liver function aspects of the study.
- **1.3** By monitoring and comparing vital signs, orthostatic blood pressures, physical exam, EKG, and labs (hematology, complete metabolic profile, and urinalysis) between the two groups. These are collected during study visits.
- 1.4 By conducting standardized assessment tools on cognition, anxiety, psychosis, sleep, daytime sleepiness, alertness, mood, fatigue, pain, impulsivity, suicidality, and motor and non-motor PD signs, restless legs syndrome, REM sleep behavior disorder, and quality of life during study visits. The change from baseline to each dose is compared. The assessment tools are:

Cognition:

- MoCA is designed as a rapid screening instrument for mild cognitive dysfunction. It assesses different cognitive domains: attention and concentration, executive functions, memory, language, visual-constructional skills, conceptual thinking, calculations, and orientation. [Freitas S, et al. 2013].
- Cognitive assessment battery:
  - Intellectual Functioning Estimate

1) Wechsler Test of Adult Reading (WTAR) - Word reading tests are an established method of establishing a premorbid estimate of verbal intellectual functioning, which will serve as an estimate of premorbid cognitive reserve.

Attention/Processing Speed/Executive Functioning

2) Grooved Pegboard Test: Manipulative dexterity, including finger speed, is assessed.
3) Symbol Digit Modalities Test (SDMT) - The SDMT is a measure of processing speed and working memory that has proven to be sensitive to cognitive impairment in MS that has both oral and written trials (only the oral trial will be administered given the anticipated difficulty patients will have with tremor). Participants are presented with a key at the top of a page pairing unique symbols with single digits. Participants are required to provide the correct digit with symbols that are presented on the rest of the page. The number of correct responses provided in 90 seconds on the oral and written trials, respectively, is recorded.

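### The pilot liver signal was cholestatic and mostly silent, yet no ALP, GGT or bilirubin threshold prompts on-treatment action, and Visit 3 liver results need not be reviewed before the dose doubles

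*Combined protocol and SAP*

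**What the plan says.** **Pilot signal.** The Discussion in Section III contrasts the pediatric programme with the open-label study: "the pattern was hepatocellular, not cholestatic as in our population". It adds that "most of the affected participants were asymptomatic" and, because enzymes were checked only at the highest dose, "it is not clear at what dose the liver enzymes became elevated". It also records that "all changes resolved with cessation of treatment".

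**What is measured.** Section IV.A, item 1.2: "Liver function tests (including Alk Phos, ALT, AST, GGT, Total Bili) will be tested at each dose during treatment phase". The panel in Section IV.D has ALT, AST, ALP and bilirubin, without GGT.

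**Liver rules.** Section IV.D: "At any time if aminotransferase enzymes are greater than three times the upper limit of normal (ULN), we will repeat" the panel within 48–72 hours. Close observation follows if symptoms persist, or if repeat ALT/AST stays above 3xULN (twofold above an elevated baseline). Hepatology is consulted unless the repeat shows aminotransferases back at baseline. Each of the four discontinuation considerations begins with an ALT or AST multiple. One rule is wider: any abnormal panel result at the end-of-treatment visit is repeated two weeks later and then until it returns to baseline.

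**General dose rule.** Section IV.C.1 ties dose to CTCAE grade: increase after grade 1, reduce after grade 2, stop permanently after a related grade 3 or 4 event.

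**Timing.** Visit 3 is on Day 3 or 4, and 2.5 mg/kg/day starts after four days at 1.25 mg/kg/day, so on Day 5.

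**The concern.** The liver rules are built around a hepatocellular pattern, whereas the sponsor's own pilot is described as showing the other one. The alternative entry to the liver rules is symptoms, which most affected pilot participants did not have. A participant with the pilot-type presentation (ALP or GGT up, no symptoms, ALT/AST at or below 3xULN) could therefore have the abnormality measured at Visit 3 without any liver-specific step following from it.

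A second gap concerns sequence and applies to every liver test. The Visit 3 blood is drawn one or two days before the dose doubles, and nothing makes the increase wait for the result.

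What is at stake is participant safety. Section III says that the hepatologist supported going on with close monitoring and that the DSMB accepted this protocol's monitoring plan, so the plan should act on the signal that prompted it.

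**Working it through.** **1. The plan's own dose comparison.** Section III states "the amount of CBD in this study is less than 15% (19.23/2.5"). The quotient is printed upside down: 19.23/2.5 = 7.69. Its inverse, 2.5/19.23 = 13.0%, agrees with the stated bound.

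**2. Which rules respond to an asymptomatic ALP, GGT or bilirubin rise with ALT/AST at or below 3xULN?**

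| Rule (section) | Responds? |
|---|---|
| 48–72 h repeat (IV.D) | No: needs ALT/AST above 3xULN |
| Close observation (IV.D) | No: needs persisting symptoms or an ALT/AST repeat |
| Hepatology consultation clause (IV.D) | No: refers to aminotransferases |
| Four discontinuation considerations (IV.D) | No: bilirubin counts only with ALT/AST above 3xULN |
| End-of-treatment repeat (IV.D) | Yes for ALP and bilirubin, but the repeat is off drug; GGT is not in that panel |
| CTCAE dose rule (IV.C.1) | Depends on grade: grade 1 increase, grade 2 reduce, related grade 3–4 stop; no retest time or consultation at any grade |
| Reduced dose by judgement (IV.C.1); adverse-event follow-up (IV.D) | Possible, but discretionary or untimed |

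Entry criteria cap AST/ALT at 3xULN but set no ALP or GGT limit, so a raised baseline ALP can enter.

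**3. Timing around the doubling.** Dose step: 2.5/1.25 = 2. A repeat 2–3 days after the draw falls on Day 5–6 (Day 3 draw) or Day 6–7 (Day 4 draw). Even the existing ALT/AST repeat is therefore on or after the Day 5 increase. A retest without a hold would not prevent escalation.

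**4. Wait for the next scheduled liver test.** Under Appendix 1 it is at Visit 4 (Day 14 to 18): 14 − 4 = 10 to 18 − 3 = 15 days after Visit 3. Section IV.C.1 places a liver test on the third to fifth day of each dose, Section IV.A item 1.1 names a "liver function monitoring visit, and safety follow up visit", and Appendix 6 lists its procedures. Figure 2 and Appendix 1 show only a phone call at that point. If the test is done on Day 7–9, the wait is 7 − 4 = 3 to 9 − 3 = 6 days. A rise first seen then would wait 14 − 9 = 5 to 18 − 7 = 11 days for Visit 4.

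**5. Exposure.**
- Daily dose at Visit 3: 1.25/19.23 = 6.5% of the pilot dose.
- Cumulative dose by the Visit 3 draw: 3 × 1.25 = 3.75 to 4 × 1.25 = 5.0 mg/kg, which is 19.5% to 26.0% of one pilot day.
- Oil at target for 84 kg: 84 × 2.5/100 = 2.1 mL/day, against 10–20 mL/day for most pilot participants.

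**6. Does a hold fit the schedule?** Assume the repeat is timed from the draw, reviewed the same or next day, and the dose raised the next morning. Review is on Day 5–8 and escalation on Day 6–9, a delay of 1–4 days. The tenth target-dose day is 6 + 9 = Day 15 to 9 + 9 = Day 18. Visit 4 may be as late as Day 18, and take-home supply is limited to 20 days.

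The sleep recording needs seven days at the maximum dose and must be done by the third night before Visit 4. In the longest case, Days 9–15 are the seven days and the night of Day 15 is the third night before Day 18, so one eligible night remains.

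**The case against.** The strongest reply is that the plan already has a mandatory brake. The CTCAE rule is not discretionary: grade 2 reduces the dose and a related grade 3–4 event stops drug. Section IV.C.1 says CTCAE governs dose adjustment immediately after scheduling the liver tests, and Section IV.C.6 notes that each event term has its own grade descriptions. A reader might infer that nothing automatic ever stops the increase after an isolated ALP, GGT or bilirubin rise. The documents do not support that. The missing hold is certain only for rises that are grade 1 or not recorded as adverse events. The general grade 1 wording, which includes asymptomatic findings, could take in a pilot-type rise. No cut-offs for these markers are printed, so the level at which the brake acts cannot be determined.

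A reader might also infer that every liver-specific laboratory rule needs an ALT/AST rise. The end-of-treatment repeat does not, and the Visit 4 sample behind it is taken after a supervised dose. That repeat comes off drug, so it does not guide dosing.

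The choice was also informed. The hepatologist reviewed the pilot liver data, the DSMB accepted the plan, Section IV.D follows FDA guidance, and its list of stopping considerations is open-ended. This argues for modest severity, but it does not supply the missing trigger. The plan itself treats ALP and bilirubin as worth repeating once treatment ends.

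Finally, a rise at Visit 3 is unlikely after so little drug. That stands, but it cannot be excluded, because the pilot did not establish the dose of onset.

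**Conclusion.** The point holds as a low-cost safety improvement. Followed as written, the liver rules give no timed on-treatment retest, consultation or hold for an isolated ALP, GGT or bilirubin rise, and Visit 3 liver results of any kind need not be seen before Day 5. What is missing is an automatic step, not access to care.

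The risk is low: 13.0% of the pilot dose at target, 14–18 days of treatment, a small oil volume, and pilot changes that reversed off drug. The between-group efficacy analysis is unaffected.

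The conclusion rests on the sponsor's own description of the pilot pattern. It does not show that the existing trigger would have missed any pilot case, which a reader might infer. The pilot ALT/AST values are not in the text available for this review, so some of those participants may also have exceeded 3xULN.

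**What to change.** 1. **Section IV.D, panel and trigger.** Add GGT to the panel. Add a trigger for ALP, GGT and bilirubin, each as a multiple of ULN or of an elevated baseline, set by the existing hepatology consultant. An example, as an assumption only, is ALP above 2xULN. It should lead to the same 48–72 hour repeat, with close observation and consultation if the rise is confirmed.
2. **Section IV.D, consultation clause.** Make it refer to whichever liver marker was abnormal.
3. **Section IV.C.1, escalation.** Require Visit 3 liver results to be reviewed and CTCAE-graded before the increase to 2.5 mg/kg/day. If any liver trigger is met, including ALT/AST above 3xULN, hold the increase until the repeat has been reviewed. The sleepiness rule in the same section already delays escalation in a similar way.

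**Cost.** A wording amendment and one set of thresholds; no new analyte, since item 1.2 already lists all of them. There will be occasional extra blood draws. Confirmed cases need the full close-observation work-up, with tests two or three times a week and exclusion of other liver disease. A hold of about 1–4 days can use the whole four-day Visit 4 allowance and leaves little room for the sleep recording. A participant who stays at 1.25 mg/kg/day is already permitted under the dose escalation strategy.
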